--	--

	
diabetes mellitus (Yes or No). The S4 assessments will become the baseline assessments. A combined visit (S4/Randomization [Baseline/Day 0]) will be recorded for all randomized subjects.
 
All randomized subjects will be provided with detailed instructions regarding when to take spironolactone, patiromer/placebo, and other baseline medications after considering the subject's current medication regimen, patiromer/placebo instructions regarding administration, and subject preference (see Section 5.5.1). The subject will be instructed to begin taking study drugs (spironolactone and patiromer/placebo) on the day following randomization (Day 1) and on the morning of their subsequent study visits to delay taking their blood pressure medications until office blood pressure measurements have been completed.
 
Treatment Period Visits (refer to Appendix A):
 
During the Double-Blind Treatment Period, study visits will occur at Week 1 (Day 8 ± 3 days), Week 2 (Day 15 ± 3 days), Week 3 (Day 22 ± 3 days), Week 4 (Day 29 ± 3 days), Week 6 (Day 43 ± 7 days), Week 8 (Day 57 ± 7 days), Week 10 (Day 71 ± 7 days), and Week 12 (Day 85 ± 7 days).
 
Patiromer/placebo treatment:
 
Patiromer/placebo will be taken at a starting dose of two packets once daily (QD). Based upon the treatment algorithm, patiromer/placebo will be increased in two-packet per day increments for local $K^+ > 5.1$ mEq/L in intervals of at least 1 week up to a maximum dose of six packets QD. For subjects with $K^+ < 4.0$ mEq/L, patiromer/placebo dose will be decreased by at least two packets per day. The minimum dose of patiromer/placebo is 0 packets. Patiromer/placebo should be taken with food, at least 3 hours before or 3 hours after administration of other oral concomitant medications including spironolactone. Refer to Appendix B (Patiromer/Placebo Titration) for complete dosing and monitoring instructions.
 
Throughout the Double-Blind Treatment Period, subjects who develop $K^+ \geq 5.5$ mEq/L that cannot be managed with blinded patiromer/placebo escalation according to the treatment algorithm (refer to Appendix B) will discontinue spironolactone and patiromer/placebo, but will remain in the study (refer to Appendix C, Spironolactone Dosing) and complete all remaining scheduled visits. After discontinuation of spironolactone and patiromer/placebo, hyperkalemia may be treated using the standard of care per the Investigator's judgment.
 
Spironolactone treatment:
 
Spironolactone will be initiated for all randomized subjects on Day 1, at a dose of 25 mg taken orally QD. At Week 3, for subjects with AOBP SBP ≥ 120 mmHg and $K^+ \leq 5.1$ mEq/L, spironolactone will be increased to 50 mg QD. For subjects with AOBP SBP ≥ 120 mmHg and $K^+ > 5.1$ mEq/L at Week 3, the 25 mg daily dose of spironolactone will be continued until the first subsequent visit when K^+ is ≤ 5.1 mEq/L (and AOBP SBP is ≥ 120 mmHg) at which time spironolactone will be increased to 50 mg QD.
 
Subjects with AOBP SBP < 120 mmHg at the Week 3 Visit will continue spironolactone at 25 mg per day.
 
If a subject has an AOBP SBP < 100 mmHg or experiences symptoms of hypotension with AOBP SBP < 120 mmHg, the spironolactone dose may be reduced (e.g., 25 mg every other day) or discontinued at the discretion of the Investigator (Appendix C, Spironolactone Dosing). If spironolactone is discontinued, patiromer/placebo must be discontinued at the same time. These subjects will remain in the study and be followed per protocol.
 
Blood pressure management:
 
When spironolactone has been discontinued and AOBP SBP is ≥ 165 to < 200 mmHg, alternative antihypertensive medication may be added to the blood pressure regimen (Appendix D, Blood Pressure Management and Alternative BP Medication

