--	--

	
Suggestions). Baseline antihypertensive medication doses should not be changed except for AE-related reasons where changes to baseline medications can be justified by the Investigator (e.g., increases in loop diuretics for new edematous states or discontinuation of baseline medication for drug-related AEs).
 
For subjects on spironolactone 25 mg QD (before Week 3), spironolactone may be increased to 50 mg QD before the Week 3 Visit for persistent SBP \geq 180 mmHg (AOBP), at the investigator's discretion. For subjects on spironolactone 50 mg QD, an additional BP medication may be added to control persistent SBP \geq 165 mmHg AOBP) at the discretion of the Investigator. This decision may reflect the degree of blood pressure elevation, the time since last spironolactone dose adjustment, and the level of urgency to lower blood pressure, in the Investigator's judgment. Baseline medication doses should not be changed except for AE-related reasons where changes to baseline medications can be justified by the Investigator (e.g., increases in loop diuretics for new edematous states or discontinuation of baseline medication for drug-related AEs).
 
For all subjects (on or off spironolactone) with AOBP SBP \geq 200 mmHg, subjects should be treated in accordance with the standard of care for BP management per the Investigator's judgment (i.e., additional medications or change in baseline medication dose are permitted, Appendix D). Note: All subjects will remain in the study and complete all study assessments in accordance with the protocol.
 
Unscheduled Visits:
 
For subjects with study drug (spironolactone or patiromer/placebo) modifications based on BP assessments or potassium levels, an Unscheduled Visit should be conducted within 1 week after this modification unless the next scheduled visit is within 1 week of the study drug modification, in which case the subject will return at the next scheduled visit.
 
Upon completion of all Double-Blind Treatment Period assessments at the Week 12 Visit (or ET Visit), subjects will discontinue all study drugs that they are receiving (patiromer/placebo/spironolactone). After study drug discontinuation, the treatment of hypertension should proceed in accordance with the standard of care for BP management per the Investigator's judgment.
 
Follow-up Visit (2 Weeks after Week 12 or ET Visit + up to 7 Days Window):
 
All subjects will be instructed to return for a Follow-up Visit 2 weeks after the Week 12 Visit or after ET Visit (+ up to 7 days). The Investigator may request the subject to return to the study site prior to the Follow-up Visit to evaluate potassium levels, BP, or AEs, at his/her discretion. If a subject arrives at the Follow-up Visit prior to 2 Weeks, subjects will receive a Follow-up Phone Call at 2 weeks (+ up to 7 days) after Week 12 or ET Visit.

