Throughout the Double-Blind Treatment Period, subjects who develop $K^+ \geq 5.5$ mEq/L that cannot be managed with blinded patiromer/placebo escalation according to the treatment algorithm (refer to Appendix B) will discontinue spironolactone and patiromer/placebo, but will remain in the study (refer to Appendix C) and complete all remaining scheduled visits. After discontinuation of spironolactone and patiromer/placebo, hyperkalemia may be treated using the standard of care per the Investigator's judgment.

Spironolactone treatment:

Spironolactone will be initiated for all randomized subjects on Day 1, at a dose of 25 mg taken orally QD. At Week 3, for subjects with AOBP SBP ≥ 120 mmHg and $K^+ \leq 5.1$ mEq/L, spironolactone will be increased to 50 mg QD. For subjects with $K^+ > 5.1$ mEq/L, 25 mg daily dose of spironolactone will be continued until the first subsequent visit when K^+ is ≤ 5.1 mEq/L (and AOBP SBP ≥ 120 mmHg), at which time spironolactone will be increased to 50 mg QD.

Subjects with AOBP SBP < 120 mmHg at the Week 3 Visit will continue their 25 mg daily dose, unless symptoms of hypotension are present with SBP < 120 mmHg, or if SBP is < 100 mmHg (Appendix C), in which case the spironolactone dose may be reduced to 25 mg every other day or discontinued altogether, at the discretion of the Investigator. Spironolactone may be reduced or discontinued for SBP < 100 mmHg. If spironolactone is discontinued, patiromer/placebo must be discontinued at the same time. These subjects will remain in the study and be followed per protocol.

Note: During all study visits, if a subject experiences symptoms of hypotension with AOBP SBP < 120 mmHg, or if SBP < 100 mmHg, spironolactone dose may be reduced (e.g., 25 mg every other day) or discontinued at the discretion of the Investigator.

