For subjects on spironolactone 25 mg QD (before Week 3), spironolactone may be increased to 50 mg QD before the Week 3 Visit for persistent SBP ≥ 180 mmHg (assessed by AOBP), at the investigator's discretion. For subjects on spironolactone 50 mg QD, additional BP medication may be added to control persistent SBP ≥ 165 mmHg (assessed by AOBP) at the discretion of the investigator. This decision may reflect the degree of blood pressure elevation, the time since last spironolactone dose adjustment, and the level of urgency to lower blood pressure, in the investigator's judgment. Baseline medication doses should not be changed except for AE-related reasons where changes to baseline medications can be justified by the Investigator (e.g., increases in loop diuretics for new edematous states or discontinuation of baseline medication for drug-related AEs).

For all subjects (on or off spironolactone) with AOBP ≥ 200 mmHg, subjects should be treated in accordance with the standard of care for BP management and the Investigator's judgment (i.e., additional medications or change in baseline medication dose are permitted, Appendix D).

Note: All subjects will remain in the study and complete all study assessments in accordance with the protocol.

Unscheduled Visits:

For subjects with study drug (spironolactone or patiromer/placebo) modifications based on BP assessments or potassium levels, an Unscheduled Visit should be conducted within 1 week after this modification unless the next scheduled visit is within 1 week of the study drug modification, in which case the subject will return at the next scheduled visit.

Upon completion of all Double-Blind Treatment Period assessments at the Week 12 Visit (or ET Visit), subjects will discontinue all study drugs that they are receiving (patiromer/placebo/spironolactone). After study drug discontinuation, the treatment of hypertension should proceed in accordance with the standard of care for BP management and the Investigator's judgment.

3.1.3 Follow-up Visit (2 Weeks after Week 12 or ET Visit + up to 7 day window)

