For subjects on spironolactone 25 mg QD (before Week 3) and $K^+ \leq 5.1$ mEq/L, spironolactone may be increased to 50 mg before the Week 3 visit for persistent SBP ≥ 180 mmHg (assessed by AOBP), at the investigator's discretion.

For subjects on spironolactone 50 mg QD (for most subjects will usually be after Week 3) or on spironolactone < 50 mg QD and $K^+ > 5.1$ mEq/L, additional BP medication may be added to control persistent SBP ≥ 165 mmHg (assessed by AOBP) at the discretion of the investigator. This decision may reflect the degree of blood pressure elevation, the time since last spironolactone dose adjustment and the level of urgency to lower blood pressure, in the investigator's judgment. Baseline medication doses should not be changed except for AE-related reasons where changes to baseline medications can be justified by the Investigator (e.g., increases in loop diuretics for new edematous states or discontinuation of baseline medication for drug-related AEs).

Suggestions for BP medications which may be added are listed below (Rossignol, 2015):

- β blockers, preferably one with an hepatic elimination route (i.e., metoprolol, carvedilol, nebivolol, and propranolol) to avoid drug accumulation, which could lead to an increased risk of bradyarrhythmias
- α blockers (e.g., doxazosin)
- Centrally acting α agonists that do not require dose adjustments (e.g., clonidine)
- Direct vasodilators (i.e., hydralazine or minoxidil) may sometimes be used, but could induce severe fluid retention and tachycardia (especially minoxidil, which has other side effects such as hirsutism and pericardial effusion).

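### Protocol Section 3.1.2 and the synopsis allow the pre-Week 3 step to spironolactone 50 mg on blood pressure alone, while Appendix D also requires K+ ≤ 5.1 mEq/L (minor)

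*Protocol*

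**What the plan says.** Three places in the protocol describe the step from 25 to 50 mg QD before Week 3.

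- Section 3.1.2, under blood pressure management: "spironolactone may be increased to 50 mg QD before the Week 3 Visit for persistent SBP ≥ 180 mmHg", measured by AOBP and at the investigator's discretion. Potassium is not mentioned.
- Synopsis, under blood pressure management: "spironolactone may be increased to 50 mg QD before the Week 3 Visit for persistent SBP" at or above 180 mmHg. Again potassium is not mentioned.
- Appendix D, under SBP 165 to below 200 mmHg with spironolactone ongoing: "For subjects on spironolactone 25 mg QD (before Week 3) and $K^+ \leq 5.1$ mEq/L", followed by the same permission at the same 180 mmHg threshold.

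The routine step at Week 3, also in Section 3.1.2, requires both AOBP SBP of at least 120 mmHg and K+ of at most 5.1 mEq/L. For subjects above that potassium level, the "25 mg daily dose of spironolactone will be continued until the first subsequent visit when" potassium has come down to 5.1 or less.

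Section 6.2.2 sends sites to Section 3.1.2 and the appendices together and does not say which prevails. Appendix D describes its content as recommendations and leaves the final decision to clinical judgment.

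**The concern.** The section that sites read first for dosing omits a potassium limit that the sponsor imposes on the same step in an appendix, and on the same dose increase at Week 3. Hyperkalemia is the risk this trial is built around, and entry eGFR is 25 to 45 mL/min/1.73 m². A rule that is looser on potassium before Week 3 than at Week 3 looks like an oversight, and no reason for it is given.

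Two things are at stake. The first is safety: an investigator could follow Section 3.1.2 and double the dose at a potassium level where the Week 3 rule withholds it. The second is conduct: Section 12.2 bars deviations without written approval, yet a monitor could not tell from the protocol whether an early step at K+ 5.3 mEq/L is a deviation.

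**Working it through.** No sample size, power or test statistic is involved, so the check is a comparison of texts plus one subtraction.

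**Conditions for moving from 25 to 50 mg QD**

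| Text | Timing | SBP condition | Potassium condition |
|---|---|---|---|
| Section 3.1.2, blood pressure management | before Week 3 | persistent ≥ 180 mmHg | none |
| Synopsis, blood pressure management | before Week 3 | persistent ≥ 180 mmHg | none |
| Appendix D | before Week 3 | persistent ≥ 180 mmHg | K+ ≤ 5.1 mEq/L |
| Section 3.1.2, spironolactone treatment | Week 3 | ≥ 120 mmHg | K+ ≤ 5.1 mEq/L |

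**Illustration.** Take a Week 2 subject on 25 mg with persistent SBP of 182 mmHg and K+ of 5.3 mEq/L. Section 3.1.2 and the synopsis permit 50 mg. Appendix D does not, because 5.3 > 5.1. The Week 3 rule would also hold this subject at 25 mg.

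**Does another sentence close the gap?**

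- The hold at 25 mg for K+ above 5.1 does not clearly reach the early step. In Section 3.1.2, Section 5.3.3 and Appendix C it follows a sentence about Week 3. The synopsis ties it to that visit outright: "mEq/L at Week 3, the 25 mg daily dose of spironolactone will be continued until the first subsequent visit when" potassium is back at 5.1 or below.
- The text of Section 5.3.3 and of Appendix C does not mention the early step.
- Section 9 ranks the SAP above the protocol. SAP Section 2.2 describes only the Week 3 increase and refers back to protocol Appendices B and C for titration, so it does not settle the matter.
- Figure 3 in Appendix C is not available. Its legend defines K+, so it probably has potassium branches; whether they cover the early step is unknown.

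**How far must SBP rise?** Inputs are the entry SBP range of 135 to 160 mmHg (Section 4.1) and the early-step threshold of 180 mmHg (Section 3.1.2).

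- Smallest rise, from the top of the range: 180 − 160 = 20 mmHg.
- From the bottom of the range: 180 − 135 = 45 mmHg.

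This rise must occur on spironolactone and must be persistent, a term the text does not define. Only the Week 1 and Week 2 visits are scheduled before Week 3.

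**The case against.** The strongest reply is that Section 3.1.2 is the summary and Appendix D the detail. Section 6.2.2 has staff review local potassium and AOBP together before adjusting doses, so the potassium value is in hand. A site that follows Appendix D satisfies every text, and the early step is optional everywhere. Much of this stands, and it is why the point is minor. It does not remove the conflict: the early-step sentence in Section 3.1.2 carries no pointer to Appendix D, and an appendix that calls itself recommendations does not plainly override the main text.

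A second reply is that harm is already contained. K+ above 5.1 mEq/L calls for more patiromer/placebo, a dose change calls for a visit within 1 week, and unmanageable K+ ≥ 5.5 mEq/L stops spironolactone. This also stands, with two limits. The visit and the stop act only after the dose has been doubled, and extra packets bind no potassium in the placebo arm, where they contain microcrystalline cellulose.

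A reader might infer three stronger claims. The documents do not support them.

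- *That Section 3.1.2 forbids an added drug for subjects below 50 mg with K+ above 5.1.* Its sentence, "For subjects on spironolactone 50 mg QD, additional BP medication may be added to control persistent SBP ≥ 165 mmHg", does not list them. But Section 5.5.2.1 permits new drugs under Section 3.1.2 and Appendix D, and Appendix D lists this group. That is an editorial omission with no consequence for subjects.
- *That the Introduction proves 5.1 mEq/L to be the safety boundary.* The highest-risk group it cites starts at K+ above 4.5 mEq/L, so the Appendix D limit would itself allow the step in part of that group. The sound argument is consistency with the sponsor's own Week 3 rule.
- *That a material number of subjects would be misdosed, or the endpoints biased.* The documents give no distribution of on-treatment SBP or potassium from which to estimate this.

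**Conclusion.** The conflict is real and minor. Section 3.1.2 and the synopsis omit a potassium limit of 5.1 mEq/L that Appendix D places on the same pre-Week 3 step and that Section 3.1.2 itself places on the Week 3 step. No text clearly resolves the difference.

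Very few subjects are likely to be affected, because SBP must rise by at least 20 mmHg from entry within the first two scheduled visits, and potassium must be above 5.1 mEq/L at the same time. That is a judgment from the entry criteria and visit schedule, not an estimate.

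The conclusion rests on the prose of the protocol. If Figure 3 does carry the potassium condition, sites are better protected than the text suggests, but the sentences in Section 3.1.2 and the synopsis would still disagree with Appendix D. The design, sample size and analysis are not in question.

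**What to change.** In the pre-Week 3 sentence of Section 3.1.2 and of the synopsis, add the condition that K+ is at most 5.1 mEq/L. Confirm that Figure 3 agrees.

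The cost is one clause in each of two sentences. The condition already stands in Appendix D and matches the Week 3 rule, so no new clinical decision is needed. Subjects excluded from the early step are not left without treatment: for those "or on spironolactone < 50 mg QD and $K^+ > 5.1$ mEq/L, additional BP medication may be added to control persistent SBP" at or above 165 mmHg, under Appendix D. Sample size, endpoints and the SAP are unaffected.

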4 SUBJECT SELECTION AND WITHDRAWAL

All potential study subjects will be evaluated using the inclusion and exclusion criteria, described below.

4.1 Inclusion Criteria

Eligible subjects must meet all the following criteria:

1. Provide written informed consent prior to participation in the study
2. Age \geq 18 years
3. Taking at least three antihypertensive medications, one of which is a diuretic, for at least 28 days at a stable dose. ACE inhibitors or ARBs should be included among these three antihypertensive medications, unless previously not tolerated or contraindicated.
4. Uncontrolled hypertension as documented by AOBP SBP 135 to 160 mmHg at each Screening Visit; however, AOBP SBP may be $<$ 135 mmHg at either S2 or S3 Visits (see Section 7.3.2.2)
5. eGFR of 25 – \leq 45 mL/min/1.73 m² (mean [calculated by the IWRS] of two values measured at S1 and S3 or 7 to 28 days apart during the Screening/Run-in and calculated using CKD Epidemiology Collaboration [CKD-EPI] formula)
6. Qualifying local laboratory K⁺ measurements of 4.3 – 5.1 mEq/L obtained at Visits S1, S3 and S4 (all measurements must be within range)
7. Females of child-bearing potential must be non-lactating, must have a negative serum pregnancy test at screening, must use a medically acceptable form of birth control from 28 days prior to screening through the study and for 28 days after completion of the study

4.2 Exclusion Criteria

Subjects must not meet any of the following criteria:

1. History of untreated secondary causes of hypertension (other than CKD) including but not limited to Cushing's syndrome, primary hyperaldosteronism, renal vascular stenosis, or coarctation of the aorta

2. Inability to measure BP (e.g., the largest sized arm BP cuff is inadequate given the circumference of the subject's arm)
3. Noncompliance with antihypertensive medications, in the investigator's judgment
4. Change in renal function requiring hospitalization or dialysis within 3 months prior to screening
5. Renal transplant or anticipated need for renal transplantation during planned study participation
6. History of malignancy within the previous 12 months except for cured non-melanocytic skin cancer
7. Recent cardiovascular event (within the last 3 months): myocardial infarction, unstable angina, hospitalization for heart failure, revascularization, or stroke (or transient ischemic attack)
8. Clinically significant ventricular arrhythmia
9. Atrial fibrillation with HR > 100 bpm
10. Previous use of patiomer in a clinical study
11. Any current use of spironolactone or other mineralocorticoid antagonists (e.g., eplerenone)
12. Hypersensitivity to patiomer, spironolactone, or any of their components
13. Use of any of the following permitted potassium-altering chronic medications if doses have not been stable for at least 28 days prior to screening or if doses are anticipated to change during study participation: bronchodilators, theophylline, heparin, and canagliflozin
14. Use of the following prohibited medications within 7 days prior to Screening: calcium acetate or calcium carbonate supplements (unless for occasional antacid use, at the discretion of the Investigator), digoxin, direct renin inhibitors (e.g., aliskiren), lanthanum carbonate, lithium, sevelamer, quinidine, sodium polystyrene sulfonate or calcium polystyrene sulfonate, colestevlam, colestipol, cholestyramine, drospirenone, potassium supplements, bicarbonate or baking soda (unless for occasional antacid use, at the discretion of the Investigator), triamterene, amiloride, trimethoprim, tacrolimus, cyclosporine, systemic glucocorticoids, nonsteroidal anti-inflammatory drugs (NSAIDs) or COX-2 inhibitors (with the exception of low dose aspirin), sympathomimetics
15. Use of any investigational product within 30 days or 5 half-lives, whichever is longer, prior to screening
16. History of bowel obstruction, swallowing disorders, clinically significant gastroparesis, severe gastrointestinal disorders or major gastrointestinal surgery (e.g., large bowel resection)
17. Inability to take the study medications or comply with the protocol, in the opinion of the Investigator
18. History of alcohol or drug abuse within 1 year of screening

19. Any medical condition, uncontrolled systemic disease, or serious intercurrent illness that would significantly decrease study compliance or jeopardize the safety of the subject or affect the validity of the trial results, in the opinion of the Investigator

